6.3 Concomitant Medication and Supportive Care Guidelines

All supportive therapy for optimal medical care will be given during the study period at the discretion of the attending physician(s) within the parameters of the protocol and documented on each site's source documents as concomitant medication.

6.4 Duration of Treatment

Patients will be on metformin treatment for approximately 14 days prior to initiation of concurrent chemo-radiation in order to complete a metformin dose- escalation phase designed to decrease metformin toxicity. Patients will then complete a 6-7 week course of metformin + concurrent chemoradiation. Patients will continued to be monitored for toxicity (phase I) for 30 days following completion of radiation treatment prior to proceeding to the next dose level in the phase I component.

6.5 Criteria for Removal from Study

Criteria for removal from the study include: intercurrent illness that prevents further treatment administration, patient's decision to withdraw from the study, progression of disease, development of a 2nd primary tumor (lung, esophagus, oral cavity, oropharynx, larynx or hypopharynx) and delay in protocol initiation and/or completion. If the protocol is discontinued, all patient follow up will continue in accordance with institutional standard of care protocols.

6.6 Duration of Follow-Up

All patients will be followed for 2 years following radiation treatment completion. In the first year, patients will be evaluated every 3 months, in the second year every 4 months which is consistent with institutional practice and clinical guidelines for the management of patients with head and neck cancer

7.0 DOSING DELAYS/DOSE MODIFICATION

7.1 **Cisplatin dose modifications.** A suggested dose modification protocol is offered below; however, treating physicians may utilize other protocols which are consistent with current standard of care for this agent.

7.1.1 Leukopenia: hold cisplatin infusion if absolute neutrophil counts (ANC) falls below 1500/ml, and proceed with radiotherapy only. Check CBC in one week, resume cisplatin at 40mg/m² if ANC \geq 1500/ml; continue to hold cisplatin infusion and proceed with radiation only if ANC less than 1500/ml.

7.1.2 Thrombocytopenia: hold cisplatin infusion if platelet counts falls below 100,000/ml, and proceed with radiotherapy only. Check CBC every week, resume cisplatin at 40mg/m² only if platelet count is over 100,000/ml, but continue radiation as scheduled.

7.1.3 Neurotoxicity: If grade 2 neurotoxicity developed, hold cisplatin (but continue RT) until toxicity improves to < grade 1, then resume cisplatin. If any signs of grade 3 or greater neurotoxicity occur, discontinue cisplatin, but continue RT.

7.1.4 Renal Adverse Events: If creatinine > 1.5 mg / dL, hydrate the patient over a 24hr period using normal saline 2000 mL + KCl 20 mEq / L + 1 gm MgSO₄ and administer the 100% dose if creatinine <1.5 mg / dL, reduce to 50% if creatinine > 1.5 mg / dL and <1.9 mg / dL. Hold cisplatin if creatinine increase to more than 1.9mg/dl, but continue on radiation as scheduled.

7.1.5 Nausea and Vomiting: Maximum supportive therapy will be given, and cisplatin will be continued at full dose for \leq grade 2 nausea and vomiting. For grade 3 nausea and vomiting refractory to supportive therapy, cisplatin will be held until recovery to < grade 2. No dose reductions will be made.

7.1.6 Mucositis: Significant mucositis (grade 3-4, CTCAE, v. 4) is expected from radiation and cisplatin and should not be a reason for a treatment break, unless it significantly interferes with fluid intake or nutrition. Aggressive supportive care is encouraged.

7.1.8 For any other grade 3-4 non-hematologic adverse events possibly related to cisplatin, hold cisplatin until toxicities have recovered to grade 1 or less.

7.2 **Metformin dose modifications.** All metformin dose modifications refer to the BID dosing. For example, “decreased by 350mg” refers to a reduction from 500mg PO BID to 250mg PO BID or from 850mg PO BID to 500mg PO BID.

7.2.1 Hypoglycemia: Although the risk of hypoglycemia in euglycemic patients receiving metformin is very low, patients in this trial might have a low caloric intake due to complications of treatment, and will undergo weekly blood glucose monitoring.

If based on these lab values or associated symptoms, the treating physician diagnoses hypoglycemia (Grade 1 or greater), study drug treatment will be halted, while concurrent chemoradiation will continue. Once blood glucose normalizes, metformin will be restarted and the dose should be decreased to the next available lower dose (see table below) with daily monitoring of blood glucose. Patients will

be provided equipment and supplies for twice daily blood glucose checks, along with a form used to record values.

Instructions for Metformin Dose Reductions due to Adverse Events	
Starting Dose (mg PO BID)	Reduced Dose (mg PO BID)
1500 mg	1350 mg
1350 mg	1000 mg
1000 mg	850 mg
850 mg	500 mg
500 mg	0 (off treatment)

If hypoglycemia resolves to < Grade 1 after 7 days, daily monitoring will be discontinued and the patient will resume the previous dose. All dose de-escalation and re-escalation will be recorded in source documentation. If **hypoglycemia** symptoms persist **for more than 7 days**, the study drug will be stopped and this will be considered a DLT.

722 Gastrointestinal toxicity: In the event of grade 2-4 gastrointestinal toxicity (typically involving flatulence or diarrhea), patients will be supported with loperamide, at dosing schedules recommended in the package insert. Gastrointestinal side effects typically subside within 4-6 weeks of initiating metformin treatment.

Efforts should be made to maintain the dose as close to the planned total daily treatment dose as much as possible. Before dose-reducing, alterations to the daily intake schedule of metformin should be taken to reduce gastrointestinal symptoms, including taking metformin with food rather than before meals.

If alterations in intake schedule are insufficient in reducing gastrointestinal toxicity to \leq grade 1, the metformin dose should be decreased to the next available lower dose for 1 week with loperamide support until symptoms subside.

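### Metformin reduction instructions disagree: from 500 mg BID, Section 7.2's example gives 250 mg and the 7.2.1 table gives 0; for hypoglycemia, Section 11's 250 mg step matches no table row

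*Combined protocol and SAP*

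**What the plan says.** All of this is current text in the combined protocol and SAP.

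- **Section 7.2 (opening).** Modifications are expressed per BID dose. As an example, a 350 mg decrease "refers to a reduction from 500mg PO BID to 250mg PO BID or from 850mg PO BID to 500mg PO BID".
- **Section 7.2.1, hypoglycemia.** Metformin is halted. Once glucose normalizes, "metformin will be restarted and the dose should be decreased to the next available lower dose (see table below". If the episode resolves within the 7-day rule, "daily monitoring will be discontinued and the patient will resume the previous dose"; if symptoms last longer than 7 days, "the study drug will be stopped and this will be considered a DLT".
- **Section 7.2.1, table.** It is headed "Instructions for Metformin Dose Reductions due to Adverse Events" and runs 1500, 1350, 1000, 850, 500, 0 mg BID. The zero is labelled as off treatment.
- **Section 7.2.2, gastrointestinal toxicity.** If changing the intake schedule is not enough, "the metformin dose should be decreased to the next available lower dose for 1 week with loperamide support until symptoms subside". Further weekly reductions follow the same rule.
- **Section 11.** After hypoglycemia, metformin is restarted at a dose 250 mg lower.
- **Section 6.1.** In its Phase I text, dose-reduction decisions rest with the PI or a listed co-investigator and use the toxicity-driven modifications in Section 7. Dose level 2 is forgone and Phase II proceeds at 850 mg BID. Lead-in dosing starts at 500 mg BID in both phases.

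**The concern.** Two people can each follow the protocol and give different doses. At 500 mg BID, one stops the drug and the other continues at 250 mg BID. After hypoglycemia at 850 mg BID, one restarts at 500 mg and the other at 600 mg. No sentence says which instruction prevails.

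The doses concerned are the ones in use. 850 mg BID is the Phase II dose named in Section 6.1. 500 mg BID is the lead-in dose, Dose level -1, and the first step down from 850 mg BID. What is at stake is consistent study-drug dosing and a clear record of why a patient came off metformin.

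**Working it through.** **1. The label in the 7.2 example.** For the first pair, 500 − 250 = 250 mg, whereas a 350 mg decrease would give 500 − 350 = 150 mg. For the second pair, 850 − 500 = 350 mg, which is right. The label therefore fits only one of the two pairs. No later instruction in Section 7 uses a 350 mg decrease.

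**2. The three instructions side by side (mg BID).**

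| From | 7.2.1 table | Table step | Section 11 (−250, hypoglycemia only) | 7.2 example |
|---|---|---|---|---|
| 1500 | 1350 | 150 | 1250 | not given |
| 1350 | 1000 | 350 | 1100 | not given |
| 1000 | 850 | 150 | 750 | not given |
| 850 | 500 | 350 | 600 | 500 |
| 500 | 0 | 500 | 250 | 250 |

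No table step equals 250 mg, so Section 11 disagrees with every row. The 7.2 example agrees with the table at 850 mg and disagrees at 500 mg.

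**3. Conflict by type of toxicity.**

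- Gastrointestinal, from 850 mg BID: table 500, example 500. No conflict.
- Gastrointestinal, from 500 mg BID: table 0, example 250. The example is the only competing text.
- Hypoglycemia, from 850 mg BID: table 500, Section 11 600.
- Hypoglycemia, from 500 mg BID: table 0, Section 11 and the example 250.

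**4. Size in dose.**

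- From 500 mg BID: 2 × 250 − 0 = 500 mg/day, or 500 × 7 = 3500 mg per week.
- From 850 mg BID, hypoglycemia only: 2 × 600 − 2 × 500 = 1200 − 1000 = 200 mg/day, or 200 × 7 = 1400 mg per week. If the 7.2.1 resume rule is followed, this lasts about one week.

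**5. Scale, for a reduction during radiation only.** Planned dose at 850 mg BID is 1700 mg/day. Section 6.2 gives courses of 6.5 weeks (45.5 × 1700 = 77,350 mg) and 7 weeks (49 × 1700 = 83,300 mg).

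- One week of the 500 mg BID difference: 3500/83,300 = 4.2% to 3500/77,350 = 4.5%.
- One week of the 850 mg BID difference: 1400/83,300 = 1.7% to 1400/77,350 = 1.8%.

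On schedule, the 500 mg BID lead-in is taken before radiation starts, so these percentages do not describe a reduction during lead-in.

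**The case against.** The best defense is that the table already governs. The 7.2 sentence explains how to read BID reductions and is not a dosing order. The operative steps in 7.2.1 and 7.2.2 both point to the next dose down, the table heading covers adverse events generally, and Section 6.1 sends dose-reduction decisions to Section 7. Section 10 describes Section 11 as the place for adverse events and risks, not as the modification rule. Decisions are also concentrated in the PI and listed co-investigators, which makes divergent practice less likely. Much of this stands, and it is why the point is minor. It does not remove the conflict: the Section 6.1 sentences sit in the Phase I text, Section 7 itself contains both the example and the table, and Section 11 is worded as an order.

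A reader might infer more than the documents support:

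- **That gastrointestinal reductions from 850 mg BID also conflict.** They do not (step 3). The 850 mg difference needs hypoglycemia, and Section 7.2.1 says "the risk of hypoglycemia in euglycemic patients receiving metformin is very low".
- **That every patient is exposed to a 4.2–4.5% difference because all start at 500 mg BID.** The percentages fit only a patient reduced during radiation.
- **That DLT counts or the 70% evaluability rule in Section 6.1 are materially affected.** A different step could in principle matter, but the documents give no event rate at 500 mg BID, so neither a large nor a small effect can be claimed.
- **That the zero row means hold, then resume 500 mg BID.** The 7-day rule makes this workable, and it is odd to be told to restart at zero. But the row plainly reads as stopping, and the text does not say otherwise.

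**Conclusion.** The text is wrong as written, and the severity is minor. The 7.2 example contradicts the 7.2.1 table at 500 mg BID and mislabels its own step. Section 11 contradicts the table for hypoglycemia at every dose. The differences are 500 mg/day from 500 mg BID and 200 mg/day from 850 mg BID, the latter for hypoglycemia only. The conclusion that the table is meant to govern is an inference from the operative wording and the Section 6.1 pointer; no precedence rule is stated. The relevance of the 850 and 500 mg rows rests on Section 6.1's decision to proceed at Dose level 1. How many patients would be affected cannot be estimated from the documents. Sample size, alpha and power are untouched.

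**What to change.** Make the 7.2.1 table the only ladder, with two edits:

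1. In Section 7.2, delete the 350 mg example, including its 500-to-250 step, and state that every metformin reduction follows the table in 7.2.1. The statement that doses are per BID intake can stay.
2. In Section 11, replace the fixed 250 mg decrease with a reduction to the next dose down in the 7.2.1 table.

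If clinicians want a 250 mg level, it should be added as a table row so that one ladder remains.

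One matter should be left to the sponsor and not settled by a wording edit: whether a patient with hypoglycemia at 500 mg BID stops metformin or is held and rechallenged. That is a clinical choice. It must also be reconciled with Section 13.1, which defines DLTs as gastrointestinal toxicity and hypoglycemia that require a dose reduction. Going from 500 to 0 plausibly meets that definition, while a hold with return to 500 may not.

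The cost is two wording changes in one amendment, with no added patients, visits or analyses.

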Absorption and Bioavailability: The absolute bioavailability of a metformin hydrochloride 500 mg tablet given under fasting conditions is approximately 50-60%. Studies using single oral doses of metformin tablets of 500 mg and 1500 mg, and 850 mg to 2550 mg, indicate that there is a lack of dose proportionality with increasing doses, which is due to decreased absorption rather than an alteration in elimination. Food decreases the extent of and slightly delays the absorption of metformin, as shown by approximately a 40% lower mean peak concentration and 25% lower area under the plasma concentration versus time curve (AUC), and a 35 minute prolongation of time to peak plasma concentration (T_{max}) following administration of a single 850 mg tablet of metformin with food, compared to the same tablet strength administered fasting. The clinical relevance of these decreases is unknown.

Distribution: The apparent volume of distribution (V/F) of metformin following single oral doses of 850 mg averaged 654 + 358 L. Metformin is negligibly bound to plasma proteins in contrast to sulfonylureas which are more than 90% protein bound. Metformin partitions into erythrocytes, most likely as a function of time. At usual clinical doses and dosing schedules of metformin hydrochloride tablets, steady state plasma concentrations of metformin are reached within 24-48 hours

and are generally ≤ 1 pg/mL. During controlled clinical trials, maximum metformin plasma levels did not exceed 5 μ g/mL, even at maximum doses.

Metabolism and Elimination: Intravenous single-dose studies in normal subjects demonstrate that metformin is excreted unchanged in the urine and does not undergo hepatic metabolism (no metabolites have been identified in humans) nor biliary excretion. Renal clearance is approximately 3.5 times greater than creatinine clearance which indicates that tubular secretion is the major route of metformin elimination. Following oral administration, approximately 90% of the absorbed drug is eliminated via the renal route within the first 24 hours, with a plasma elimination half-life of approximately 6.2 hours. In blood, the elimination half-life is approximately 17.6 hours, suggesting that the erythrocyte mass may be a compartment of distribution.

Special Populations

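### Sections 7.2.1 and 13.1 define the hypoglycemia DLT incompatibly, and the 7-day clause in 7.2.1 has no stated start and would rarely register metformin-related hypoglycemia

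*Combined protocol and SAP*

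**What the plan says.** Section 7.2.1 sets out a sequence for hypoglycemia of Grade 1 or greater, diagnosed from laboratory values or symptoms:

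- At diagnosis, "study drug treatment will be halted, while concurrent chemoradiation will continue".
- The restart rule that follows reads: "Once blood glucose normalizes, metformin will be restarted and the dose should be decreased to the next available lower dose", with daily glucose monitoring. The reduction table runs from 850 mg to 500 mg twice daily, and from 500 mg to off treatment.
- If the event falls below Grade 1, then "after 7 days, daily monitoring will be discontinued and the patient will resume the previous dose".
- If symptoms persist "for more than 7 days", the section's consequence is that "the study drug will be stopped and this will be considered a DLT".

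Three other sections bear on this:

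- **Section 13.1** names the Phase I DLTs as gastrointestinal toxicity and hypoglycemia that makes a dose reduction necessary. It sets no duration.
- **Section 6.1** sends the reader to 7.2 for the DLTs. It says that only patients who complete at least 70% of the planned dose during radiation are used to establish absence of DLT under the 13.2 table.
- **Section 11** gives a similar halt, restart and monitoring sequence without a DLT clause. It makes hypoglycemia a secondary Phase I measure in all patients.

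**The concern.** Hypoglycemia is one of only two toxicity types that feed the BOIN table in 13.2. According to 13.1, the move to BOIN was made so that toxicity would be monitored beyond the Phase I cohort. The table can only act on what is counted as a DLT.

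Under 7.2.1 alone, an episode that clears when metformin is halted is not a DLT. Nor is a recurrence after the previous dose is resumed, and no limit on such cycles is stated. A patient who recurs at 500 mg and goes off treatment is also not a DLT unless symptoms exceed 7 days. Under 13.1, nearly all of these patients would count. Two people applying the same protocol to the same records could therefore reach different BOIN decisions.

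**Working it through.** **1. The two definitions applied to the same events**

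| Event | 7.2.1 | 13.1 |
|---|---|---|
| Resolves on halting, restarted one level lower | Not a DLT | DLT |
| Recurs after the previous dose is resumed, resolves again | Not a DLT | DLT |
| Recurs at 500 mg, goes off treatment, symptoms 7 days or less | Not a DLT | DLT (if stopping counts as a reduction) |
| Symptoms beyond 7 days | DLT | DLT (if a reduction was made or the drug stopped) |

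The 13.1 column follows because 7.2.1 itself directs a reduction at restart.

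**2. The start of the clock**

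*From diagnosis.* If the drug stays off for the whole 7 days (168 h), the half-lives in 10.1 give the fraction remaining as 0.5^(168 / half-life):

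- Plasma, 6.2 h: 168/6.2 = 27.1 half-lives, leaving 7.0 × 10⁻⁹.
- Blood, 17.6 h: 168/17.6 = 9.5 half-lives, leaving 0.0013, or 0.13%.

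On this reading, symptoms beyond 7 days would mostly not be driven by metformin. These figures do not apply if the drug is restarted within the week.

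*From restart.* The patient is on the reduced dose, so metformin-related symptoms can meet the clause. Restart requires normal glucose, however, and a new diagnosis during that week would appear to trigger the halt again. The text does not say which instruction prevails.

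**3. The plan's BOIN boundaries**

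Inputs: target φ = 0.3 (13.1), with package defaults φ₁ = 0.6φ = 0.18 and φ₂ = 1.4φ = 0.42 (assumed, not stated in the plan).

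- Escalate: ln(0.82/0.70) / ln[(0.30 × 0.82)/(0.18 × 0.70)] = 0.2365.
- De-escalate: ln(0.70/0.58) / ln[(0.42 × 0.70)/(0.30 × 0.58)] = 0.3585.

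Both match 13.2, as do the tabulated counts for 3 to 27 patients. The table is not at issue here. The input to it is.

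**4. How much the definition matters**

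The documents give no rate for either toxicity, so these are assumptions: gastrointestinal DLT 10%; hypoglycemia leading to dose reduction 0% to 30%, independent of it; all patients at one dose; looks at 3, 6, …, 24 and 28 patients, with the last tabulated column used at 28. The combined rate is 1 − (1 − 0.10)(1 − h). At h = 0.20 it is 1 − 0.90 × 0.80 = 0.28.

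For the first cohort, the chance of 2 or more DLTs in 3 patients is:

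- Rate 0.10: 3(0.10²)(0.90) + 0.10³ = 0.028.
- Rate 0.28: 3(0.28²)(0.72) + 0.28³ = 0.191.

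An exact binomial recursion over all looks gives the chance of ever reaching a boundary:

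| Hypoglycemia rate | DLT rate if every such episode counts | De-escalation boundary | Elimination boundary |
|---|---|---|---|
| 0% | 10% | 4.0% | 0.3% |
| 5% | 14.5% | 9.6% | 1.0% |
| 10% | 19% | 18.8% | 3.0% |
| 20% | 28% | 47.9% | 15.3% |
| 30% | 37% | 78.5% | 44.2% |

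If no hypoglycemia is counted, the first row applies whatever the true rate. Elimination is shown because, at the lowest dose level, 13.2 answers a de-escalation signal with three more patients unless the level has been eliminated.

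**The case against.** A reader might infer that metformin-related hypoglycemia can never enter the toxicity count. The documents do not support that, for three reasons:

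- Section 13.1 sits in the statistical section behind the BOIN table and would count nearly every diagnosed episode.
- The order of steps in 7.2.1, and the parallel text in Section 11, fits a 7-day window that runs on the reduced dose after restart. Ending daily monitoring and resuming a previous dose describe a patient already back on drug. Restart depends on glucose and the DLT clause on symptoms, so the two can diverge.
- The washout figures need a full week off drug.

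These points stand, and they limit the claim to a clause that rarely registers such events.

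The 70% rule in 6.1 also offers partial protection. Take a cycle of 1 day off (assumed), 7 days at 500/850 of the dose, then t days at full dose. The proportion taken is (4.12 + t)/(8 + t), which is below 0.70 when t is under about 4.9 days. Such fast recurrences could not be counted as DLT-free. But they would not be counted as DLTs either.

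Finally, all adverse events are recorded and go to the Data Review Committee, 6.1 now forgoes escalation to dose level 2, and the plan expects hypoglycemia to be very uncommon. This lowers the practical stakes. It does not settle the count, because the 13.2 table uses DLTs and its de-escalation and elimination limits still apply.

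**Conclusion.** The concern holds as a conflict of definitions together with an insensitive, incompletely specified clause. Section 7.2.1, to which 6.1 points, counts few hypoglycemic episodes. Section 13.1 counts nearly all of them. Nothing in the plan says which governs, or when the 7 days begin.

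The gap could be large. At the assumed 10% and 20% rates, the chance of reaching a de-escalation boundary by 28 patients is about 4% under one extreme and about 48% under the other. If hypoglycemia is as rare as the plan expects, the gap is small: 4.0% against 9.6% at a 5% rate. These figures rest on assumed rates, independence of the two toxicities, and the extremes of counting none or all of the dose-reducing episodes. They show sensitivity to the definition and do not predict the trial's results.

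**What to change.** Reconcile 7.2.1 (the halt and restart steps and the 7-day clause), 6.1 and 13.1 into one hypoglycemia DLT definition, and name it as the one used with the 13.2 table. State when the 7-day clock starts, whether recurrences after restart or after the previous dose is resumed count, and whether going off treatment for hypoglycemia counts. Then recount DLTs from the events already recorded and check the BOIN decisions against the recount.

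Which trigger, halt, restart and resume steps apply is for the sponsor's clinical team. No clinical rule is proposed here, and the 7-day clause need not be removed. The cost is a short text change in three sections and a review of existing records. The downside is that the DLT count may rise.
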